## Statistical Analysis Plan

---

### **11.8. VITAL SIGNS**

Observed and change from baseline values will be summarized for all vital signs data (blood pressure, heart rate, respiratory rate and temperature) by treatment group and protocol specified time points using descriptive statistics.

Vital signs data will be listed by treatment group.

### **12. INTERIM ANALYSES**

A Month 12 cut of the data will be analysed and reported in the CSR. When all subjects have completed (or discontinued) the 12 Month assessment visit the data collected up to and including these study visits will be cleaned and reported. The exception to this will be SAEs and AESI where all available events up to the last subjects Month 12 visit date will be included in the report. Any changes to the data reported in this Month 12 cut will be fully auditable and discussed in the addendum to CSR that will be generated on the final 18-month study data.

An external, independent Safety Monitoring Committee (SMC) will review cumulative unmasked safety data and will have the responsibility to conduct a thorough safety assessment after the first 20 subjects have completed the Day 7, Month 2 and Month 6 visits. A key responsibility of the SMC will be to make a recommendation whether to continue, modify or stop the study based upon an evaluation of emerging safety data, in particular AESI. Additional regular or ad-hoc safety reviews will be scheduled as recommended by the SMC.

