The planned length of participation in the study for each subject is approximately 18.5 months (from Day –14 through completion of the Month 18 (Day 540) follow-up procedures).

The study is planned to take place over approximately 28 months (from screening of the first subject through completion of the last subject’s exit visit).

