### **2. INTRODUCTION**

This statistical analysis plan (SAP) for study POT-CP121614 is developed based on the final protocol version 3.0 and CRF version (20th January 2016). The purpose of this SAP is to ensure that the data listings, summary tables and figures which will be produced, and the statistical methodologies that will be used, are comprehensive and appropriate for the analysis of study objectives specified in the protocol. Any amendments to the SAP will be made prior to database lock. Any additional analyses not described in the final SAP or deviations from the final SAP will be documented in the clinical study report (CSR).

This SAP supersedes the protocol in all specifications associated with data analyses and statistical methodologies.

Study POT-CP121614 has a 12-month treatment period with an additional 6-month follow-up period. The main database lock for the study will occur when all subjects complete the Month 12 visit or have withdrawn earlier from the study and the data have been collected and cleaned. The CSR will summarize data up to 12 months. All post Month 12 follow-up data collected prior to the database lock may be presented on key safety outcomes. When all subjects complete the study (i.e. the final follow-up visit at Month 18) or have withdrawn earlier from the study and all data are collected and cleaned, the final database lock will occur. An addendum to the CSR will be developed to summarize the additional follow-up data. For key endpoints, the summary will include data for the overall study period (treatment + follow-up).

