### **4.3. SAFETY ENDPOINTS**

#### **4.3.1. Adverse Events**

The primary safety endpoints for the study are the number and severity of treatment emergent adverse events (TEAEs) and adverse events of special interest (AESI). AESI will be identified on the eCRF at the time of reporting and include:

- Endophthalmitis
- 4+ ocular inflammation
- 2-3+ ocular inflammation that fails to decrease to 1+ or less within 30 days of the onset of the event
- Sustained (> 5 minutes) loss of light perception after APL-2 (or Sham) injection
- Sustained elevation of IOP (30 mmHg) at/past 90 minutes post-injection
- Any elevation of IOP requiring surgical intervention (i.e. paracentesis)
- New vitreous hemorrhage of > 2+ severity that does not resolve within 14 days of the onset of the event
- Progression to exudative (wet) AMD in the study eye or fellow eye requiring surgical intervention (Note: Intravitreal administration of anti-VEGF agents are not considered surgical interventions.)

A clinical review of all ocular AEs will be performed prior to database lock to ensure all AESI have been identified.

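### Read together, SAP 12 and 11.1 let the SAE and AESI percentages of the Month 12 report cover 12 to 18 months per subject, against 12 months for other adverse events

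*SAP*

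**What the plan says.** SAP 12 (Interim Analyses) sets two limits for one report. Once every subject has reached or missed Month 12, "the data collected up to and including these study visits will be cleaned and reported", which means each subject's own Month 12 visit. The exception is "SAEs and AESI where all available events up to the last subjects Month 12 visit date will be included in the report", which is a single calendar date for the whole trial.

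SAP 2 (Introduction) is worded differently. It states: "The CSR will summarize data up to 12 months". It then adds: "All post Month 12 follow-up data collected prior to the database lock may be presented on key safety outcomes". This is optional, and its limit is the database lock, which comes after the last Month 12 visit.

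SAP 11.1 lists subjects with any TEAE, any serious TEAE and any TEAESI in one overall summary and adds TEAE and TEAESI totals to the same table. It gives no cut-off for the serious or special-interest rows. SAP 6.1 makes the number of subjects in the group the default denominator for percentages. Exposure-adjusted incidence is specified only for macular neovascularization (SAP 8.2.2). SAP 4.3.1 makes AESIs part of the primary safety endpoint.

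**The concern.** Protocol 11.4 collects adverse events until the subject completes the study, which is at Month 18, or leaves early. Under the SAP 12 exception, a subject enrolled early can contribute up to 6 more months of SAE and AESI follow-up, and the last subject enrolled contributes none. Other adverse events stop at Month 12 for everyone.

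A percentage of subjects with an SAE or AESI would then be neither a 12-month nor an 18-month risk, and its value would depend on how fast the trial enrolled. It could not be read against the other adverse event rows, or against another trial's 12-month figure, without knowing the follow-up behind it. Safety is a primary objective, and Protocol 5.1 says the results are to support Phase III development, so the absolute incidences matter. SAP 2 and SAP 12 also differ on whether later events must be shown and up to what date.

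**Working it through.** **Inputs from the documents.** Protocol 8.1: "The study is planned to take place over approximately 28 months" and "The planned length of participation in the study for each subject is approximately 18.5 months", the latter running from Day -14 to Day 540. Follow-up ends at Month 18, 6 months after Month 12. Protocol 11.3.4 assumes 15-20% loss to follow-up.

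**1. The plan's own figure.** (14 + 540)/30 = 18.47 months, which agrees with the stated 18.5.

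**2. Implied accrual.** 28 - 18.5 = 9.5 months.

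**3. Nominal SAE/AESI window.** Let e be the time from a subject's Month 12 visit to the last subject's Month 12 visit, capped at 6 months. With uniform accrual (assumption), e = min(6, U), where U is uniform on (0, 9.5).

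- Mean e = (6²/2)/9.5 + 6 × (9.5 - 6)/9.5 = (18 + 21)/9.5 = 4.11 months.
- Mean window = 12 + 4.11 = 16.1 months, and 16.1/12 = 1.34.
- Share of subjects at the 18-month cap = 3.5/9.5 = 37%.

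**4. Sensitivity to accrual.** With 9.5 months of accrual, linearly rising enrolment gives a mean window of 15.0 months and linearly falling enrolment gives 17.2. Uniform accrual over 6 to 14 months gives 15.0 to 16.7.

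**5. After the planned loss.** Loss is taken as exponential, reaching 15% or 20% by Month 12 and continuing at the same rate; accrual is uniform.

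| Loss by Month 12 | Other AEs, mean months | SAEs/AESIs, mean months | Ratio |
|---|---|---|---|
| 15% | 11.1 | 14.4 | 1.30 |
| 20% | 10.8 | 13.9 | 1.29 |

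**6. Illustration for SAEs.** Assume a constant hazard, no loss and uniform accrual. With r the 12-month risk and h = -ln(1 - r)/12, the reported proportion is the mean of 1 - exp(-h(12 + e)). An assumed r of 10%, 20% or 30% would be shown as 13.2%, 25.8% or 37.9%.

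**7. Where the added time falls.** It all follows the last scheduled injection, which is given at the Month 12 visit itself (Day 360 in the flow charts). Part of it lies within one dosing interval of that injection:

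- Monthly arms: mean of min(1, e) = (0.5 + 8.5)/9.5 = 0.95 months, and 0.95/4.11 = 23%.
- Every-other-month arms: mean of min(2, e) = (2 + 15)/9.5 = 1.79 months, and 1.79/4.11 = 44%.

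**8. The 60-day limit.** In SAP 11.1 this limit, as worded, applies to worsening of events present before dosing. If it were applied to all events, the mean nominal window would be 12 + (2 + 15)/9.5 = 13.8 months.

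**The case against.** The exception is disclosed and has a good purpose: serious events known at the time of reporting should not be held back. It also captures events in the days after the Month 12 injection, when Protocol 4.3 notes the risk of endophthalmitis. The addendum will give the 18-month data, and neovascularization, the signal already identified, has an exposure-adjusted analysis. These points stand. They support showing the later events, but not pooling them into a percentage without a defined window.

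Several stronger readings are tempting, and the documents do not support them:

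- *The table certainly mixes the windows.* SAP 12 says only that the events go into the report. They could be confined to the separate SAE and AESI listings that SAP 11.1 plans. Mixing in one table is inferred from SAP 11.1, which gives no separate cut.
- *The added time is almost wholly off treatment.* Step 7 shows otherwise.
- *The percentages are diluted.* A cumulative proportion of subjects can only rise with longer follow-up. At most a contrast between arms could be diluted.
- *A subject whose only event is an SAE at Month 15 counts as serious but not under any TEAE.* This assumes a filter that the SAP does not state; a serious TEAE is also a TEAE.
- *The constant-hazard figures apply to AESIs.* Several AESIs are defined by the injection, such as loss of light perception after it or raised pressure 90 minutes later. For these the effect is likely smaller than for SAEs.

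SAP 2 is permissive and can be read as compatible with SAP 12. The two still differ on whether later events must be shown and on the cut-off date.

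**Conclusion.** The point holds. The two cut-offs are explicit in SAP 12, and SAP 11.1 does nothing to separate them or to supply person-time. Unless the tables add a rule that the SAP does not contain, the SAE and AESI percentages rest on a window of 12 to 18 months set by enrolment date, against 12 months for other events.

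The nominal mean is about 16 months, and after the planned loss the comparison is about 14 against 11 months, a ratio of about 1.3. These sizes rest on the planned 28-month timeline, on uniform accrual and, for the second comparison, on exponential loss. The 60-day reading would shorten the window.

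A reader might infer bias between the arms. The documents do not support that: randomisation is blocked within sites, so the arms should have similar enrolment dates. The harm is to absolute incidences and to comparison across rows. The correction is worth making because it is cheap and bears on part of the primary safety endpoint.

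**What to change.** - In SAP 12 and 11.1, use one cut for all TEAE, SAE and AESI rows of the main summary tables: each subject's Month 12 visit, or withdrawal if earlier.
- Report SAEs and AESIs after that visit, including those following the Month 12 injection, in a separate post-Month 12 table with patient-years and in a listing, both in the same clinical study report.
- Align SAP 2 with SAP 12 on whether later events are shown and on the cut-off date.
- SAP V3.0 was written after the 12-month results had been reviewed (SAP 4.1 and 8.1.3). If the Month 12 tables already exist, apply the change in the addendum.

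The cost is SAP wording, one filter in the table programs and one extra table. No new data are needed and no event is hidden. The downside is that events soon after the Month 12 injection move from the main table to the separate one, so the main table should carry a footnote pointing to it.

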### **13. CHANGE FROM ANALYSIS PLANNED IN PROTOCOL**

The changes from the analyses specified in the protocol are:

1. The definition of the PP population has been updated to exclude any subject who has violated any inclusion or exclusion criteria and/or deviated from the protocol, in a way that could influence their efficacy assessment. The protocol refers to the PP as all randomized subjects who return for 12 month visit which is simply a completer's analysis which is covered in the sensitivity analyses of the primary endpoint.
2. The primary analysis specified in the protocol does not take account of baseline in the model, however as a precaution baseline has been included in the model. If there is no relationship with baseline then only one degree of freedom is lost by including this term in the model.
3. The protocol specified the use of ANOVA on the data at Month 12 with missing data handled by the LOCF or by a non-precise regression method of imputation when imbalance drop-out rates occur across treatment groups. An MMRM approach, which directly utilizes

## Statistical Analysis Plan

---

all available data in the model, has been specified in the SAP to account for missing data and this will be regarded as the primary analysis.

4. The pharmacokinetic endpoints of AUC,  $C_{max}$ ,  $T_{max}$  and  $t_{1/2}$  were specified in the protocol; however since only trough concentrations were collected throughout the study it is only possible to assess  $C_{max}$ .  $C_{max}$  should occur at Day 7 so the concentration on Day 7 will be used ( $C_{Day 7}$ ).
5. The protocol specified a standard deviation of annual square root area growth of 0.21mm/year for the sample size calculations. However in the power analysis (protocol Section 11.3.3) a value of 0.2 was used for the standard deviation.
6. The protocol refers to the first day of dosing as Day 0 (Visit 2). For reporting purposes CDISC standards will be used and therefore it is necessary to refer to the first day of dosing as Day 1. Consequently throughout the SAP Day 1 is referred to as the first day of dosing.

## Statistical Analysis Plan

---

